#### **Study Day**

The study day for all assessments prior to the first study drug administration is calculated as the difference between the date of the event or measurement (e.g., AE onset date, assessment date, sample collection date, etc.) and the start date of study treatment. The day before the start of study treatment is Study Day -1.

The study day for all post assessments after the first study drug administration is calculated as the difference between the date of the event or measurement (e.g., AE onset date, assessment date, sample collection date, etc.) and the start date of study treatment, plus one day. The first day of study treatment is Study Day 1.

#### **Baseline**

Baseline value is defined as the valid and last non-missing value obtained within 14 days prior to subject receiving the first study medication, unless otherwise stated under the related

assessment section. Baseline can be the day before the first study medication or on the same day as the first study medication if a pre-dose assessment is available. Subjects without data on a parameter before the first study medication will have a missing baseline for this parameter.

### **Handling of Incomplete or Missing Data**

Missing data will not be imputed in general and it will be reported as missing in all listings. For categorical variables, patients with missing data are not included in calculations of percentages unless otherwise specified.

#### **Missing start and end dates for AE and concomitant medication (CM)**

The assumption will be the worst or most conservative judgment when imputing AE and CM start and end dates. The purpose of imputing a start date is to help define whether the AE/CM started while taking study drug.

For a partial or missing start date:

- If the day is missing, the first day of the month will be imputed. If the missing day is the same as the month of first dose of study drug, then the first dose date will be imputed.
- If the day and month are missing, the first day of January will be imputed. If the year is the same as the first dose date, then the first dose date will be imputed.
- If the day is completely missing, the first dose date will be imputed. If the end date suggests it could have started prior to this, the first day of January of the same year as the end date will be imputed.
- When imputing a start date, the start date will ensure that the new imputed date is sensible, i.e., is prior to the end date of the AE or CM.

For a partial or missing end date:

- If the day is missing, the last day of the month or the last assessment date, whichever is earlier, will be imputed.
- If the day and month are missing, the 31st of December or the last assessment date, whichever is earlier, will be imputed
- If the date is completely missing, there will be a need to look at whether the AE/CM is still ongoing before imputing a date. If the ongoing flag is missing, then it will be assumed that AE is still present, or CM is still being taken (i.e., do not impute a date). If the AE/CM has stopped, then the last assessment date will be imputed.

These data imputations are for categorization purpose only and will not be used in listings.

If the assessment of the relationship of the AE to KD025 is missing, then the relationship to KD025 has to be assumed and the AE considered as such in the frequency tables of possibly related AEs, but no imputation should be done at the data level.

### **Missing event dates**

Event date will be imputed only when day is missing, and the purpose of imputing an event date is to most conservatively calculate time to event.

If the day is missing, the first (mid, last) day of the month will be imputed for undesired (neutral, desired) event. If the missing day is the same as the month of first dose of study drug, then the first dose date will be imputed for undesired event.

These data imputations are for time to event calculation only and will not be used in the listings.

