## **3.8 Efficacy Endpoints and Analyses**

### **3.8.1 Primary Efficacy Endpoint: ORR**

The primary efficacy endpoint is the overall response rate, with response status as assessed by investigators based upon the 2014 NIH Consensus Development Project on Clinical Trials in cGVHD (see Protocol Appendix F: cGVHD Response Assessment).

Response is assessed using individual scores from ten systems (Skin, Eyes, Mouth, Esophagus, Upper GI, Lower GI, Liver, Lungs, Joints and Fascia and Global Severity Rating (GSR)). Response is assessed with respect to the baseline (Cycle 1, Day 1 (C1D1)) cGVHD assessment. The overall response at each assessment time point will be categorized as Complete Response (CR), Partial Response (PR), or Lack of Response (LR), where LR includes the response status of unchanged, mixed, or progression as defined in [Table 2](#).

The ORR is defined as the proportion of subjects with a best response meeting the overall response criteria assessment of CR or PR at any post-baseline response assessment.

If a treated subject is lost to follow up without response assessment, this subject will be counted as a non-responder. Any response on and after new systemic cGVHD treatment will be censored as non-response.

Point estimates, various confidence intervals (Clopper-Pearson (exact) method) listed in Figure 2, and raw and Hochberg adjusted p-values corresponding to the null hypothesis of  $ORR \leq 30\%$  vs alternative hypothesis of  $ORR > 30\%$  by treatment arms will be reported.

The number and percentage of subjects who have a best response of PR and number and percentage of subjects who have a best response of CR will also be reported.

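### A missing event day is set to the first of the month with no bound at the last event-free contact, so a death or new therapy can be dated on or before a visit showing it had not yet happened

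*SAP*

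**What the plan says.** SAP 3.14, Missing event dates, imputes an event date only when the day is missing: "If the day is missing, the first (mid, last) day of the month will be imputed for undesired (neutral, desired) event". There is one exception, for undesired events: "If the missing day is the same as the month of first dose of study drug, then the first dose date will be imputed". The section gives its aim, "the purpose of imputing an event date is to most conservatively calculate time to event", and its scope: "These data imputations are for time to event calculation only and will not be used in the listings".

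Undesired events enter the secondary endpoints as follows:

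- **DOR:** new systemic therapy and death are events under all four definitions (SAP 3.8.2.1 and the censoring table there, Table 3).
- **TTNT:** new systemic therapy (SAP 3.8.2.5).
- **FFS:** new systemic therapy, non-relapse mortality and recurrent malignancy (SAP 3.8.2.8).
- **OS:** death (SAP 3.8.2.9).

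The DOR table has a re-dating rule. When lack of response or new therapy follows two or more missed assessments, the event is placed four weeks after the last documented assessment.

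**The concern.** The rule looks at the calendar month and the first dose date. It does not look at what the site recorded during that month. If the participant attended a visit on the 20th, alive and not on new therapy, and an event is later reported for that month without a day, the rule still dates the event to the 1st. The analysis dataset then contradicts the response and visit listings.

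Two things are at stake. First, some event times are shortened by more than the record allows. Second, when the first response falls in the same month as the event, DOR comes out negative. A negative duration cannot enter a Kaplan-Meier estimate as it stands, so someone must drop it, set it to zero or re-date it, and the SAP does not say which. A same-month response and event imply a true DOR of at most 30 days. Dropping such cases would therefore remove very short durations and lengthen the estimated DOR, which is the opposite of the rule's stated aim.

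Partial dates are plausible because long-term follow-up is by telephone, e-mail, post or medical records (Protocol 6.2.8).

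**Working it through.** The plan gives no figure for this rule, so there is none to reproduce.

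**Inputs**

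- Undesired event with a missing day: dated to the first of the month (SAP 3.14).
- Spacing g between contacts: 28 days, then 56 days, for on-treatment response assessments (Protocol 3.1); about 84 days in long-term follow-up (Protocol 6.2.8).
- Assumptions, not in the documents: the true event day is uniform over the calendar, and the last event-free contact lies u days earlier, with u uniform on 1 to g.

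**Step 1: size of the back-dating.** If the true day of the month is D, the shift is s = D − 1. A month of L days contributes L(L − 1)/2 to the sum of s: 465 for 31 days (seven months), 435 for 30 days (four) and 378 for 28 days (one).

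Mean s = (7 × 465 + 4 × 435 + 378)/365 = 5373/365 = 14.7 days. The maximum is 30.

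**Step 2: imputed date on or before the last event-free contact.** This happens when s ≥ u, with probability E[min(s, g)]/g.

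- g = 28: s exceeds 28 by 1 on the 30th (11 months) and by 2 on the 31st (7 months), so (5373 − 11 − 14)/365 = 14.65, and 14.65/28 = 0.523.
- g = 56: 14.72/56 = 0.263.
- g = 84: 14.72/84 = 0.175.

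**Step 3: strictly before the contact.** This requires s > u. Of the 365 days, 353 are not the first of a month, so E[max(s − 1, 0)] = (5373 − 353)/365 = 13.75.

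- g = 28: s − 1 exceeds 28 by 1 on the 31st (7 months), so (5020 − 7)/365 = 13.73, and 13.73/28 = 0.490.
- g = 56: 13.75/56 = 0.246.
- g = 84: 13.75/84 = 0.164.

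**Step 4: simulation, and the effect of a floor.** A calendar simulation of 400,000 events per spacing agrees. It also gives the mean back-dating when the imputed date may not be earlier than the day after the last event-free contact.

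| Spacing | On or before | Strictly before | Mean shift, as written | Mean shift, with floor | Difference |
|---|---|---|---|---|---|
| 28 days | 0.523 | 0.490 | 14.7 | 9.2 | 5.5 |
| 56 days | 0.264 | 0.247 | 14.7 | 11.9 | 2.8 |
| 84 days | 0.1746 | 0.163 | 14.7 | 12.9 | 1.8 |

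The text uses the simulated values rounded to whole percentages: 52%, 26% and 17%; strictly before, 49%, 25% and 16%. The strict figures are the plain contradictions, because a therapy could start later on the day of a visit.

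**Step 5: worked example.** First partial response is on 20 March. New therapy is reported for March with the day unknown, and the true day is 28 March. True DOR is 28 − 20 = 8 days. The imputed date is 1 March, so computed DOR is 1 − 20 = −19 days. With the floor the date is 21 March and DOR is 1 day.

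**Step 6: does the DOR table repair this?** No. Its re-dating needs two or more missed assessments. The contradiction arises when the visit was attended.

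**The case against.** The strongest defence is that early dating is intended. The SAP says so, and for DOR, TTNT, FFS and OS the shift goes against the drug. It is at most 30 days per event. SAP 3.2 makes all secondary endpoints descriptive, and alpha goes only to ORR, so no test is affected. The percentages are conditional on a missing day. The largest of them applies to 28-day on-treatment visits, where the site is recording cGVHD therapies and partial dates are least expected; for telephone or mail follow-up the relevant figure is about 17%. In DOR, deterioration and lack of response take the date of the assessment itself, and the table anchors some other events to a documented assessment. All of this stands and limits the size of the point. It does not justify a date that the record rules out: the earliest date consistent with the record is still conservative, and it avoids negative durations.

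A reader might infer three stronger things that the documents do not support.

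- **That the rule turns responders into non-responders in the primary endpoint.** SAP 3.8.1 says "Any response on and after new systemic cGVHD treatment will be censored as non-response", so a therapy back-dated to the 1st would seem to cancel a response on the 10th. But the imputed dates are confined to time-to-event calculation, ORR is a proportion, the ORR rule does not call on imputed dates, and the general rule is "Missing data will not be imputed in general and it will be reported as missing in all listings". What remains is a silence: the SAP does not say how a therapy with an unknown start day is ordered against a response in the same month.
- **That there is no lower bound at all.** The first dose date is one. The missing bound is at the last event-free contact.
- **That the event rule is laxer than the one for adverse events and concomitant medication.** That rule's check is that "the start date will ensure that the new imputed date is sensible, i.e., is prior to the end date of the AE or CM". It compares a start date with the same record's own end date, not with visits, and a death has no end date.

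**Conclusion.** The point holds as a minor defect in a stated rule. Followed exactly, it permits event dates that contradict attended visits and can produce a negative DOR, with no instruction for handling one. Among missing-day events the imputed date falls on or before the last event-free contact in about 52%, 26% or 17% of cases at 28-, 56- or 84-day spacing. The avoidable part of the back-dating averages about 5.5, 2.8 or 1.8 days per such event.

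These figures rest on uniform event days and uniform contact timing. They describe conflict with the last event-free contact. A negative DOR is a narrower case, because the first response must fall in the event month. The documents do not say how many partial dates to expect. The number is probably small, so no change in a median or landmark rate can be claimed. ORR is not affected by the rule as written.

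**What to change.** Amend SAP 3.14, Missing event dates, for undesired events: impute the latest of the first of the month, the first dose date, and the day after the last documented event-free assessment or contact, but not beyond the last day of the reported month. Define event-free by endpoint: known alive for death, and documented free of new systemic therapy for a therapy start.

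Add one clarifying sentence, in the same section or in SAP 3.8.1, that imputed dates do not reclassify a documented response in ORR. This only makes explicit what the scope statement already implies.

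The cost is two sentences and one extra comparison in the derivation program. No new data are needed, because visit and contact dates are already collected. The rule stays conservative, since it still takes the earliest date that the record allows, to within a day.

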## 5 APPENDIX A: Tables, Listings and Figures (TLFs)

**Table 3: Demographics and Baseline Characteristics TLFs**

T/F/L	Title	Population
T	Patient disposition	miITT
L	Patient disposition	miITT
L	Protocol deviations	miITT
T	Demographics and baseline characteristics	miITT
L	Demographics and baseline characteristics	miITT
T	Medical histories by primary system organ class and preferred terms	miITT
L	Medical history	miITT
T	cGVHD and transplant history	miITT
L	cGVHD and transplant history	miITT
T	Summary of organ involvement at baseline and baseline score	miITT
T	Summary of prior systemic cGVHD therapy	miITT
L	Prior systemic cGVHD therapy	miITT

**Table 4: Efficacy TLFs**

T/L/F	Title	Population
Primary Endpoint: ORR		
T	Overall Response Rate*	miITT
T	Overall response rate (ORR) for responses occurring within 6 months of treatment	miITT
T	Overall response rate (ORR) for responses occurring within 12 months of treatment	miITT
T	Landmark ORR at 6 months	miITT
T	Landmark ORR at 12 months	miITT
F	Forest plot of ORRs (1. all subjects in an arm, subgroups within arm; 2. Two arm combined if ORRs of those two arms are similar)	miITT

 In all tables, figures and listing, results will be presented by two treatment arms and overall, unless otherwise specified.

T/L/F	Title	Population
L	Listing of overall response by subject by visit	miITT
Secondary Endpoint: DOR		
T	Descriptive Kaplan-Meier and landmark (12, 20, 24, 32, 36, 48 weeks) statistics for DOR*	Responder
F	Kaplan-Meier plot of DOR*	Responder
L	Listing of all DOR episodes for each subject	Responder
Secondary Endpoint: TTR		
T	Descriptive statistics for cumulative response rate over time (TTR)	Responder
F	Cumulative response rate over time (TTR)	Responder
L	Listing of TTR for each subject	Responder
Secondary Endpoint: LSS score		
T	Descriptive statistics for LSS score for: a) number of subjects with a 7-PtR from baseline; b) number of subjects with 7-PtR on 2 consecutive assessments; c) DO7-PtR (<8, 8-16, 16-24, 24-32, 32-40, 40-48, >48 weeks)	miITT, Responder, Nonresponder
T	Summary of LSS Score (overall and each of seven domains) raw and change from baseline by visit	miITT, Responder, Nonresponder
F	Summary of Lee Symptom Scale Score (overall and each of seven domains) raw and change from baseline by visit	miITT, Responder, Nonresponder
L	Listing of Lee Symptom Scale Score by subject, domain and visit	miITT
Secondary Endpoint: Response by Organ System		
T	Best response by individual organ	miITT
T	Organ responses according to baseline NIH / severity score	miITT
L	Listing of organ score and response assessment by subject and visit	miITT
T	Descriptive statistics for cumulative response rate over time (TTR) by organ	miITT, Responder
F	Cumulative response rate over time (TTR) by organ	miITT, Responder
Secondary Endpoint: Corticosteroid Dose		
T	Descriptive statistics for prednisone equivalent dose of corticosteroids for a) change and % change from baseline to greatest reduction; b) the number and % subjects who reduced dose; c) number and % subjects who discontinued corticosteroid usage	miITT, Responder, Nonresponder, BL corticosteroid dose level (upper and lower 50 th percentiles)

T/L/F	Title	Population
T	Descriptive Kaplan-Meier statistics for time to corticosteroid discontinuation	miITT
T	Summary of raw and change from baseline on prednisone equivalent dose of corticosteroids by visit	miITT, Responder, Nonresponder, BL corticosteroid dose level (upper and lower 50 th percentiles)
F	Box plot of prednisone equivalent dose of corticosteroids over time	miITT, Responder, Nonresponder, BL corticosteroid dose level (upper and lower 50 th percentiles)
L	Listing of all the steroid raw and standardized dosing by subject and visit	miITT
Secondary Endpoint: CNI Dose		
T	Summary of descriptive statistics for CNI for a) the number and % subjects who reduced dose from baseline; b) number and % subjects who discontinued CNI	miITT
L	Listing of all the CNI dosing by subject and visit	miITT
Secondary Endpoint: FFS		
T	Descriptive Kaplan-Meier and landmark (6, 12, 18 and 24 months) statistics for FFS (with cumulative failure rates for each of the 3 components FFS)	miITT
F	Kaplan-Meier plot for FFS (with cumulative failure rates for 3 components of failures)	miITT
L	Listing of failure events	miITT
Secondary Endpoint: OS		
T	Descriptive Kaplan-Meier and landmark (6, 12, 18 and 24 months) statistics for OS	miITT
F	Kaplan-Meier plot of OS	miITT
Secondary Endpoint: Symptom activity using the cGVHD Activity Assessment Patient Self-Report		
T	Descriptive statistics of change from baseline in symptom activity based on cGVHD Activity Assessment Patient Self Report (global rating) by visit	miITT

T/L/F	Title	Population
T	Descriptive statistics of symptom activity based on cGVHD Activity Assessment Patient Self Report (change of cGVHD symptom to a month ago) by visit	miITT
L	Listing of symptom activity based on cGVHD Activity Assessment Patient Self Report	miITT
Exploratory Endpoints		
T	Overall Response Rate (KARA)	miITT
T	Concordance of overall response between investigator determined responses and KARA	miITT
T	Descriptive Kaplan-Meier and landmark (12, 20, 24, 32, 36, 48 weeks) statistics for DOR (KARA)	Responder
F	Kaplan-Meier plot of DOR (KARA)	Responder
T	Best response by individual organ (KARA)	miITT
T	Descriptive statistics of change from baseline in PROMIS scale by visit	miITT, Responder, Nonresponder
T	Summary table of univariate modeling	miITT

\* Repeat TLF for subgroups of:

- Prior ibrutinib (Yes / No)
- Severe cGVHD at baseline (Yes / No)
- Number of organs involved at baseline (<4 / ≥4)
- Number of prior lines of therapy (≤3 / >3)
- Duration of cGVHD before enrollment (by 50th percentile)
- Baseline corticosteroid dose level (by 50th percentile)
- Lung involvement at baseline (Yes / No)
- Proton pump inhibitor (PPI) on C1D1 (Yes/No)
- Gender
- Age (<65 / ≥65 years )
- Race
- Prior ruxolitinib (Yes / No)
- Best response to the last prior treatment (SD/PD)
- Take concomitant medication proton pump inhibitor (PPI) on C1D1 (Yes/No)
- Baseline GFR (<60, 60-90 and ≥90 mL/min)

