21 APPENDICES

21.1 APPENDIX A: SCHEDULE OF ASSESSMENTS

Table 6 - Schedule of Assessments

Assessment	Screening	Baseline ^k	Cycle 1 Day 15	28-Day Treatment Cycles ^l	End of Treatment (EOT)	28-Day Follow-Up (±7 days)	Long Term Follow-Up (LTFU)
Cycle Day	-14 to -1	C1D1	C1D15 (±3 days)	CxD1 (±3 days)			
Written Informed Consent/Assent	X ^a						
Participant Demography	X						
Medical History	X						
Transplant History	X						
GVHD History	X						
cGVHD Prior Treatments	X						
Inclusion/Exclusion Criteria	X						
cGVHD severity assessment	X						
Randomization ^b		X					
Efficacy Assessments							
Clinician-reported global cGVHD activity assessment		X		X	X		
Response Assessment				X	X		
Pulmonary Function Tests ^c	X	X		X	X		
cGVHD Activity Assessment - Patient Self Report		X		X	X		
Lee Symptom Scale Score		X		X	X		
PROMIS Global Health Score		X		X	X		
Document Corticosteroid Dosage	Corticosteroid dosage to be collected from the date the ICF/assent form is signed until 28 days after last dose of study drug						
Document other cGVHD therapies	Other cGVHD therapies to be collected from the date the ICF/assent form is signed until 28 days after last dose of study drug						

Assessment	Screening	Baseline ^k	Cycle 1 Day 15	28-Day Treatment Cycles ^l	End of Treatment (EOT)	28-Day Follow-Up (±7 days)	Long Term Follow-Up (LTFU)
Cycle Day	-14 to -1	C1D1	C1D15 (±3 days)	CxD1 (±3 days)			
Follow-Up Contact ^d							X
New Treatment for cGVHD or underlying disease							X
Safety Assessments							
Complete PE ^e	X						
Symptom directed PE		X	X	X	X	X	
Vital signs ^f	X	X	X	X	X	X	
Weight	X	X	X	X	X		
Karnofsky / Lansky Performance Scale score	X	X		X	X	X	
Hematology	X	X	X	X	X	X	
Clinical Chemistry	X	X	X	X	X	X	
Virology ^g	X						
12-Lead ECG ^h (Table 10)	X ^h	X ^h		X ^h	X ^h	X ^h	
Highly sensitive urine or serum pregnancy test ⁱ	X	X		X	X	X	
Concomitant medications / procedures	Concomitant medications / procedures to be collected from the date the ICF/assent form is signed until 28 days after last dose of study drug.						
Adverse events	AEs to be collected from the date the ICF/assent form is signed until 28 days after last dose of study drug.						
Investigational Product							
Study drug administration		X ^j	X ^j	X ^j			
Dispense/Collect Study Drug & Study Drug Diary		X		X	X		
Pharmacokinetics	See Table 7 Table 7 and Table 8						
Pharmacodynamics	See Table 9						

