**SIGNATURE PAGE**

## DOCUMENT HISTORY

Version	Author	Description
1.0	██████████	Original Document
2.0	██████████	
Revision according to “KD025-213_Protocol Amendment 1_26Jun19_FINAL”
 
The primary reasons for this new version include:
 

• Change of study design: add a formal interim analysis with alpha spending .0025

• Change definitions of duration of response in accordance with FDA type B meeting held on 01 May 2019

• Rearrange and add some secondary efficacy endpoints

• Add subgroup analysis for proton pump inhibitor

2.1	██████████	
The primary reasons for this new version include:
 

• Add censoring rule of new systemic cGVHD treatment for organ and overall response, corticosteroids usage and Lee symptom score

• Change term of “Sponsor Assessments” into “Kadmon Algorithmic Response Assessments (KARA)”

• Add some additional analyses (section 3.8.2.12)

• Add analyses of PROMIS for responder and nonresponder populations

• In subgroup analyses: add baseline GFR, change age into <65 / ≥65 from by 50 percentile

• Clarify response assessment in appendix B

• Minor typo and wording changes

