**Figure 2 ORR Multiplicity Adjustment**

Simulations were conducted with various hypothetical ORR scenarios for two arms of 63 subjects, by using the Hochberg procedure for multiplicity adjustment; results (10000 runs per setting) are presented in [Table 1](#).

Only descriptive statistics will be provided for all secondary and exploratory endpoints, without multiplicity adjustment.

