### **3.8.2.6 Corticosteroid dose**

Corticosteroid doses will be presented as mg/kg/day prednisone equivalent dose. Descriptive statistics for the mITT population, responder /nonresponder populations and subgroups defined by baseline corticosteroid dose level (upper and lower 50 percentiles) will be provided for:

- Systemic corticosteroid dose over time
- Change and % change from baseline (C1D1) to the greatest corticosteroid dose reduction during KD025 treatment period
- Number and % of subjects who reduced systemic corticosteroid dose during KD025 treatment period

- Number and % of subjects who ever discontinued systemic corticosteroid usage for over 28 days during KD025 treatment period

The above analyses will be censored on or after new systemic cGVHD treatment.

If subjects are not using prednisone as the systemic corticosteroid, then the prednisone dose equivalent will be determined according to following conversion ratios:

1 mg prednisone is equivalent to:

- 4mg Hydrocortisone
- 0.8mg Methylprednisolone
- 0.15mg Dexamethasone
- 1mg Prednisolone
- 0.8mg Triamcinolone

Transient increases in corticosteroid dosing (not exceeding 1mg/kg/day prednisone equivalent, are permitted for the treatment of cGVHD flare, but dose must be reduced back to the pre-randomization dose within 6 weeks. If the dose remains elevated for more than 6 weeks, this will be considered a KD025 treatment failure. More than 2 episodes of cGVHD flare requiring increased corticosteroid therapy in the first 6 months of KD025 treatment will also be considered a KD025 treatment failure.

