### **3.8.2.12 Additional Analyses**

Additional analyses will be presented including:

- ORR and DOR for responses occurring within the first 6 and 12 months of treatment with KD025
- Organ responses according to baseline NIH / severity score
- Landmark FFS with CR/PR at 6 months and at 12 months
- Time to corticosteroid discontinuation

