#### **Reporting of Numerical Values**

Continuous data will be described using descriptive statistics: number of observations (n), mean, standard deviation, median, minimum and maximum. Frequencies and percentages will be used for summarizing categorical data. When categorical data are presented, the percent will be suppressed when the count is zero in order to draw attention to the nonzero counts. The denominator for all percentages, unless otherwise specified, will be the number of subjects in the specified analysis population or group.

Means, medians, standard deviations, and confidence intervals will be reported to one decimal place more than the data reported on the case report form (CRF) or by the laboratory/vendor. Minimum and maximum will be reported to the same number of decimal places displayed on the CRF or by the laboratory/vendor. P-values will be reported to 4 decimal places.

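### Time to corticosteroid discontinuation is planned as a Kaplan-Meier summary with no competing-event rule, so one minus the curve is likely to overstate the chance of coming off steroids

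*SAP*

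**What the plan says.** SAP 3.8.2.12 lists "Time to corticosteroid discontinuation" among the additional analyses and says nothing more about it. Table 4 in SAP Appendix A, in the corticosteroid block, assigns it "Descriptive Kaplan-Meier statistics for time to corticosteroid discontinuation" in the mITT population.

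Four other passages bear on it.

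- SAP 3.8.2.6, after its list of corticosteroid summaries: "The above analyses will be censored on or after new systemic cGVHD treatment". The SAP document history for version 2.1 describes the change more broadly: "Add censoring rule of new systemic cGVHD treatment for organ and overall response, corticosteroids usage and Lee symptom score".
- Protocol Appendix A, Table 6: "Corticosteroid dosage to be collected from the date the ICF/assent form is signed until 28 days after last dose of study drug".
- SAP 3.8.2.6 also plans a crude count: "Number and % of subjects who ever discontinued systemic corticosteroid usage for over 28 days during KD025 treatment period". The default denominator in SAP 3.14 is the whole analysis population or group: "The denominator for all percentages, unless otherwise specified, will be the number of subjects in the specified analysis population or group".
- SAP 3.2 sets the inferential status: "Only descriptive statistics will be provided for all secondary and exploratory endpoints, without multiplicity adjustment".

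The SAP is more explicit for other time-to-event endpoints. It gives censoring rules for duration of response, time to next therapy and failure-free survival, and the Table 4 entry for failure-free survival asks for cumulative failure rates by component.

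**The concern.** A participant who dies can no longer come off steroids. One who starts new systemic cGVHD therapy can no longer do so on belumosudil alone, because Protocol 5.8 makes new therapy a treatment failure that ends study drug. If these participants are censored, Kaplan-Meier assumes that they would have gone on to stop steroids at the same rate as those still being followed on treatment. That is implausible for people whose treatment has just failed. One minus the curve then estimates a probability in a hypothetical setting without failures, while a reader will take it as the share of participants who came off steroids.

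Protocol 3.1 uses changes in steroid dosage, among other endpoints, to support the clinical meaning of response. The report would also carry two steroid-free figures, the Kaplan-Meier estimate and the crude percentage, with no stated reason for any difference between them.

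**Working it through.** **Figure to reproduce.** The documents state no steroid-discontinuation rate, so there is none.

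**How each event is handled.**

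| Event | What the documents say for this endpoint |
|---|---|
| New systemic therapy | Censored for the summaries listed in SAP 3.8.2.6. The document history describes the rule as covering steroid usage in general. The time-to-event analysis itself is listed elsewhere, in 3.8.2.12. |
| Death | No rule. A Kaplan-Meier routine censors it unless told otherwise. |
| Stopping belumosudil | No rule. Steroid data end 28 days after the last dose (Protocol Table 6), so follow-up for this event ends soon afterwards. |

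**Direction.** At each time when steroids are stopped, one minus Kaplan-Meier grows by S_KM × d/n, where d/n is the fraction of those at risk who stop. The Aalen-Johansen cumulative incidence grows by S_all × d/n, where S_all is survival free of both the event and the competing events. S_all is never above S_KM. One minus Kaplan-Meier is therefore never below the cumulative incidence, and it is above it whenever a competing event precedes later discontinuations.

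**Size, on assumed rates.** Take constant cause-specific hazards hs (steroid stop) and hc (competing event):

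- 1 − KM = 1 − exp(−hs·t)
- CIF = hs/(hs + hc) × [1 − exp(−(hs + hc)·t)]

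With hs = 2% and hc = 5% per month and t = 12 months:

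- 1 − KM = 1 − exp(−0.24) = 21.3%
- CIF = (2/7) × [1 − exp(−0.84)] = 0.2857 × 0.5683 = 16.2%
- excess = 5.1 points

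At the ends of a range with hs 1.5% to 3% and hc 3% to 8% per month:

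| hs, hc per month | Excess at 6 months | Excess at 12 months |
|---|---|---|
| 1.5%, 3% | 0.7 points | 16.5% − 13.9% = 2.6 points |
| 3%, 8% | 3.3 points | 30.2% − 20.0% = 10.2 points |

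Competing hazards of 3% to 8% per month correspond to net 12-month probabilities of 1 − exp(−0.36) = 30% to 1 − exp(−0.96) = 62%, which is high. A second range starts lower. It sets the 12-month 1 − KM at 20% to 40% and the net 12-month competing probability at 5% to 50%:

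| 1 − KM | Net competing probability | CIF | Excess |
|---|---|---|---|
| 20% | 5% | 19.5% | 0.5 points |
| 30% | 10% | 28.6% | 1.4 points |
| 30% | 20% | 27.1% | 2.9 points |
| 30% | 40% | 23.8% | 6.2 points |
| 40% | 50% | 29.7% | 10.3 points |

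**Check.** A simulation of 200,000 participants gave 30.1% (1 − KM) against 23.9% actually off steroids for the 30%/40% row, and 30.1% against 28.7% for the 30%/10% row.

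**The case against.** The strongest reply is that the SAP never says that death or stopping belumosudil is censored. The estimator's name does not settle this, because participants with a competing event could be kept at risk to the end of follow-up. The rule in 3.8.2.6 refers to the analyses above it, and this endpoint appears later. This stands in part: for death and for stopping belumosudil, censoring is an inference. For new therapy the broader wording in the document history makes it the natural reading, and nothing in the SAP points to the alternative.

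Three further objections stand.

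- **The crude percentage.** A reader might infer that the proportion coming off steroids will be overstated. The SAP reports that proportion separately, and with the default denominator this mechanism does not inflate it. Only one minus Kaplan-Meier is affected. A difference between the two figures would not itself prove an error, because under staggered entry and administrative censoring the cumulative incidence also differs from a crude percentage.
- **Weight.** This is an additional, descriptive analysis with no alpha. Table 4 names neither landmark times nor a plot for it, unlike duration of response and failure-free survival. Protocol 3.1 and 11.7.2 refer to change in steroid dose, not to time to discontinuation.
- **Stopping belumosudil.** It is not always a failure. Protocol 4.8.1 includes loss to follow-up, sponsor termination and, for adults, having received more than 6 months of treatment. Protocol 6.2.5 provides for participants who leave without entering the rollover study. Coding every such exit as a competing event would bias the estimate downwards.

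A reader might also infer that the gap is always larger in the arm with more failures. It depends on the steroid-stopping rate as well. A net competing probability of 30% with 1 − KM of 40% gives 5.8 points, while 40% with 1 − KM of 20% gives 4.2 points.

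**Conclusion.** The point holds for the Kaplan-Meier summary. The plan names that estimator with no competing-event rule, applies censoring at new systemic therapy to its steroid analyses, and is silent on death. If both are censored, the direction of the error is certain: one minus Kaplan-Meier overstates the probability of coming off steroids. Its size in this trial cannot be computed. Over the assumed ranges it is about 0.5 to 10 points at 12 months, and the upper end needs frequent competing events.

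The endpoint is also under-defined. The SAP gives no event definition, time origin or at-risk set. Inclusion criterion 3 in the current protocol permits corticosteroids without requiring them, so the mITT may include participants with no steroid to stop. The documents do not support a claim that the crude discontinuation percentage is wrong or that the ORR conclusion is at risk.

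**What to change.** In SAP 3.8.2.12 and the matching row of Table 4:

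1. Replace the Kaplan-Meier summary with the Aalen-Johansen cumulative incidence of steroid discontinuation, by arm and overall.
2. Restrict the at-risk set to mITT participants on systemic corticosteroids at baseline, and measure time from first dose.
3. Define the event by the same rule of more than 28 days off steroids that 3.8.2.6 uses for its count.
4. Treat death and new systemic cGVHD therapy as competing events.
5. Censor at data cut, rollover, other administrative end of participation and loss to follow-up.
6. State in advance whether stopping belumosudil for treatment failure or an adverse event counts as a competing event or as censoring, and give the alternative as a sensitivity analysis.

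The cost is a few lines of SAP text and a different estimator on data already collected. The reported steroid-free rate will be somewhat lower, and restricting to baseline steroid users reduces the number analysed.
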